10.3.2.2. New participants with acute HIV diagnosis

Participants who enroll into MERLIN immediately after acute HIV diagnosis will initiate ART treatment within 72 hours after the enrollment visit and will have follow-up visits following Peruvian clinical care guidelines.

10.3.3 Last study visit

The planned last study visit is not a particular numerical week, but rather will occur on or before December 31, 2022. All participants may remain involved in MERLIN for approximately 5 years, regardless of interval between the two studies.

10.3.4 Definitions of evaluations and special indications

10.3.4.1 Medical History

A medical history must be present in source documents. The medical history should be comprehensive and include HIV-1 related and non-related diagnoses. The medical history from SABES Step 3 should be reviewed and updated if appropriate. HIV uninfected and chronic HIV infection participants should have a medical history collected.

10.3.4.2 Medication History

A medication history must be present in source documents, including any history of antiretroviral medication, immune-based therapy, or HIV-1-related vaccines, including blinded study medications.

All prescription medications taken within 30 days prior to study entry, including actual or estimated start and stop dates, should be included in both the source documents and on the case report forms (CRFs).

All nonprescription medications taken within 30 days prior to study entry, including actual or estimated start and stop dates, should also be included in source documents.

10.3.4.3 Concomitant Medications

All of the concomitant medications taken since the last report should be registered in the source documents and the CRF and should include the start and end dates.

10.3.4.4 Modifications of Study Treatment Regimen

All of the pharmacologic modifications including the initial doses begun by the subject and/or interruptions proscribed by the protocol, modifications, and permanent suspension of the treatment should be recorded at ever visit in the source documents and the CRF

10.3.4.5 Clinical Assessments

1. Complete physical exam

A complete physical exam is to be performed at study entry and study completion.

2. Targeted physical exam

A targeted physical examination is required as clinically indicated.

3. Height to be collected at study entry.

4. Weight to be collected at all study visits.

5. Vital signs

Oral temperature, pulse, and blood pressure to be collected at all visits.

6. Waist circumference should be measured at the enrollment (or the following visit) when the sample for lipid panel and glucose (fasting) is taken, as well as during week 144 and 216.

7. Signs and symptoms

All signs, symptoms, and toxicities at entry must be documented in the subject's record and on the CRFs. Unless otherwise specified, after entry, only grade ≥ 3 and all signs and symptoms that led to a change in treatment, regardless of grade, must be recorded on the CRFs. The "Division of AIDS Table for Grading the Severity of Adult and Pediatric Adverse Events Version 1.0, December, 2004; Clarification August 2009" must be used and is available at <http://rsc.tech-res.com/safetyandpharmacovigilance>.

8. Diagnoses

All confirmed and probable diagnoses made since the last visit must be recorded in the source documents and CRFs. The following diagnoses will be recorded in source

documentation and CRFs: U.S. Center for Disease Control and Prevention Category B and C diagnoses, major organ disease including but not limited to diabetes, cardiovascular disease and stroke, hepatitis, avascular necrosis, fat redistribution including central fat accumulation and peripheral fat wasting (as noted by subject and site staff and/or primary care provider). Please refer to AIDS Clinical Trials Group Appendix 60 for specific diagnoses and definitions which can be found at <http://www.hptn.org/web%20documents/HPTN052/Appendix60V1.123Feb2007.pdf>.

9. Neuropsychiatric Testing

As part of the assessment of neuroinflammation in acute/recent HIV, each participant will undergo neuropsychiatric testing during each study visit. The visit will follow Study specific procedure (SSP) for neuropsychiatric testing.

10.3.4.6 Questionnaires

Questionnaires will be self-administered by participants at each visit (every 24 weeks). The questionnaire will take approximately 60 minutes in each visit.

This questionnaire will contain several modules:

1. Drug and alcohol use [drug use history, DAST 10 (drug abuse screening test) , drinking expectancies];
2. Mental health and well-being [RAND 12 (health well-being) , Social support scale, Stigma scale, Stigma and diagnoses disclosure, Partner notification, Intimate partner violence, 10 item CES-D (depression scale), Mental health items on anxiety, Stress & Coping];
3. Medical care (hospitalization and ER use, Barriers to care, Access to care, Self-efficacy for ART use).

10.3.4.7 Laboratory Assessments

The “Division of AIDS Table for Grading the Severity of Adult and Pediatric Adverse Events Version 1.0, December, 2004; Clarification August 2009” must be used and is available at <http://rsc.tech-res.com/safetyandpharmacovigilance>.

All baseline laboratory values must be documented in the subject's record and recorded on the CRFs. Subsequently, all laboratory values must be documented in the subject's record, but unless otherwise specified, only laboratory values Grade ≥ 3 must be recorded on the CRFs. Any laboratory toxicity that led to a change in treatment, regardless of grade, must be recorded on the CRFs. Laboratory evaluations that do not have a grading scale in the “Division of AIDS Table for Grading the Severity of Adult and Pediatric Adverse Events Version 1.0, December, 2004; Clarification August 2009” must be collected on the CRFs if the values are outside the upper or lower limit of normal

1. Hematology

Hemoglobin, white blood cell count, absolute neutrophil count, platelets;

2. Blood chemistries

Serum amylase, lipase, bicarbonate, phosphorus, creatinine, AST (SGOT), ALT (SGPT),

alkaline phosphatase.

3. Lipid panel and glucose

Subjects should be fasting for at least 8 hours for blood sample collection for lipid panel and glucose measurements. These tests will be performed in the enrollment visit and follow-up visits week 144 and 216. If the participant is not fasting, the tests must be deferred and will be taken during the next programmed visit.

Triglycerides, total cholesterol, HDL, LDL and glucose.

4. Urinalysis

Dipstick, and microscopic exam if dipstick is positive;

Additionally urine samples will be stored for future drug analyses and STD tests.

5. Sexually transmitted infection testing

Syphilis screening testing will be conducted by RPR and confirmed by MHA-TP if reactive. Syphilis diagnosis will follow Ministry of Health of Peru guidelines. A positive leukocyte esterase test by a urine dipstick will trigger a microscopic examination.

Samples will be stored for further confirmation with a nucleic acid amplification test for *N. gonorrhoeae* and *C. trachomatis* if a diagnosis of urethritis is made. The results of these tests will be for research purposes only.

Participants with a positive leukocyte esterase test and/or with symptoms will receive treatment following the local standard of treatment.

10.3.4.8 Immunologic Studies

1. CD4+/CD8+ T-cell subsets

A CD4+ T-lymphocyte percent of total lymphocytes and CD8+ T-lymphocyte percent of total lymphocytes should be performed in addition to the absolute CD4+ and CD8+ T cell counts at screening and for all visits at which CD4+/CD8+ T cell counts are required. Because of the diurnal variation in CD4+ and CD8+ cell counts, determinations for individual subjects should be obtained consistently in either the morning or the afternoon throughout the study, if possible.

NOTE: Each time a CD4+/CD8+ measurement is obtained, the local laboratory must perform a WBC and differential from a sample obtained at the same time.

10.3.4.9 Virologic Studies

1. Plasma HIV-1 RNA

All HIV-1 RNA testing will be performed using the Abbott m2000 RealTime System (Abbott Molecular) at the IMPACTA PERU Clinical Trials Unit Central Laboratory, which is certified by the U.S. NIH/NIAID/DAIDS Virology Quality Assurance (VQA) Program. The baseline value will be the HIV-1 RNA level at the entry evaluation.

The results from the analysis of Plasma HIV-1 RNA at each 24-weekly visit will be available at the next follow-up visit to guide the medical management decision-making for each participant, according to the HIV management standards. Samples for HIV-RNA taken more frequently (from SABES timepoints) will not be used clinically and will only be used for research purposes and therefore will not be processed in real time.

2. HIV-1 genotype in stored samples will be performed by the University of Washington Virology Specialty Laboratory/Seattle Children's Hospital at the end of the study or when required per clinical judgment at time of suboptimal virologic response.

10.3.4.10 Leukapheresis

A subset of MERLIN participants (N = 40) will undergo leukapheresis. There is a separate consent form and only those who are newly enrolled and volunteer for this procedure will have it performed. Qualitative and quantitative assessment of the HIV reservoir (including its localization in different CD4⁺ T cell subsets) will require large numbers of cells, which is important as both size and distribution of the HIV reservoir will be key factors in strategies to induce a functional cure. Thus, we will use leukapheresis to collect large samples at critical time points (SABES baseline and 24 weeks on all participants, then 72, 120, and 216 weeks for deferred arm, and 96, 144, and 196 weeks for immediate Arm).

10.3.4.11 Stored Plasma, PBMC, Whole Blood in RNA later

At all time points, whole blood, plasma, and PBMC will be stored for later analysis, many of which are described in the analysis plan, or else are for future studies as per specimen repository consents.

10.3.4.12 Stool Samples

Stool will be collected (25g per visit) at the visits indicated in the procedures table, for the evaluation of the microbiome throughout phases of VIH infection (acute-recent- and treated HIV infection) In one of the collaborative studies associated to this study, stool samples were collected. If these participants are enrolled in MERLIN they will be asked to provide stool samples in all the visits; however, for those participants who were not enrolled in the collaborative study and for who stool sample was not collected previously, only one sample will be requested during week 168 for the participants in the immediate SABES 3 arm, and during week 192 for those enrolled in the deferred SABES 3 arm.

10.3.4.13 Rectal Biopsies and Rectal Secretions

Rectal biopsies will be performed in a subset of 60 participants who additionally consent, using a separate informed consent procedure, to up to 4-3 rectal biopsies. Rectal secretions will be collected via a swab or sponge at the time of biopsy. In Immediate arm participants, the biopsies will be performed at 96, 144 and 192; ; in the Deferred arm, biopsies will occur at 120, 168 and 216 weeks. Biopsy procedure will be performed following the SSP.

10.3.4.14 Lumbar Puncture (LP)

A subset of up to 40 participants, ideally evenly dispersed between Immediate and Deferred Arms will undergo lumbar puncture to obtain cerebrospinal fluid (CSF). Those approached for CSF evaluation will sign a separate informed consent for this procedure and no MERLIN participants will undergo LP without signing a consent. LP will be performed in the specified visits as indicated in the table of procedures. Refer to the SSP for LP procedures.

11. WARNINGS AND PRECAUTIONS

11.1 LACTIC ACIDOSIS/SEVERE HEPATOMEGALY WITH STEATOSIS

Lactic acidosis and severe hepatomegaly with steatosis, including fatal cases, have been reported with the use of nucleoside analogs alone or in combination with other antiretrovirals. A majority of these cases have been in women. Obesity and prolonged nucleoside exposure may be risk factors. Particular caution should be exercised when administering nucleoside analogs to any patient with known risk factors for liver disease; however, cases have also been reported in patients with no known risk factors.

Treatment with co-formulated EVG/COBI/FTC/TAF should be suspended in any patient who develops clinical or laboratory findings suggestive of lactic acidosis or pronounced hepatotoxicity (which may include hepatomegaly and steatosis even in the absence of marked transaminase elevations).

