12.1.3 Symptomatic Hyperlactatemia

Occurrence of lactic acidosis is expected to be very rare with the medication regimen used in this protocol. However, if an investigator suspects – due to symptoms or lab abnormality – lactic acidosis or symptomatic hyperlactatemia, a lactate level should be drawn.

Symptomatic hyperlactatemia will be defined as new, otherwise unexplained and persistent occurrence for >2 weeks of one or more of the following in addition to an elevated lactate level:

- nausea and vomiting
- abdominal pain or gastric discomfort
- abdominal distention
- increased LFTs
- unexplained fatigue
- dyspnea
- motor weakness

If the lactate value is $> 2 \times$ ULN, obtain a confirmatory lactate value as soon as possible, preferably within 1 week. Study treatment should be discontinued immediately if the confirmatory value remains $> 2 \times$ ULN or if the site is unable to obtain a confirmatory value within 1 week. Determine lactate levels every 4 weeks until the lactate value returns to normal, at which time a new antiretroviral regimen may be constructed in consultation with the protocol team.

Management of symptomatic lactate value $< 2 \times$ ULN will proceed at the discretion of the local investigator. However, any modification of a subject's antiretroviral regimen should be made in consultation with the protocol team.

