12.2 LABORATORY TOXICITIES

Laboratory results will be flagged by the laboratory as abnormal or critical using pre-determined criteria at the laboratory. Abnormal values will be confirmed by repeat testing of the same specimen. All critical values will be reported to On-Site Principal Investigator by cell phone or e-

mail. All results will be documented in laboratory records. All laboratory test results will be reported.

Participants who are not present at the study site at the time a critical value is identified will be contacted by telephone or in person and asked to come back to the study site for further evaluation, referral, and counseling.

Grade 3 and 4 laboratory abnormalities should be confirmed by repeat testing preferably within 3 calendar days of receipt of results and before study drug discontinuation, unless such a delay is not consistent with good medical practice. All laboratory abnormalities that would lead to a change in treatment should be confirmed as soon as possible.

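### On suspected lactic acidosis, section 11.1 suspends treatment while section 12.1.3 states no stop before a confirmatory lactate, and the protocol does not say which governs

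*Protocol*

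**What the plan says.** Section 11.1, under Warnings and Precautions, notes that deaths have been reported with this class of reaction. It then states: "Treatment with co-formulated EVG/COBI/FTC/TAF should be suspended in any patient who develops clinical or laboratory findings suggestive of lactic acidosis". The sentence goes on to cover pronounced hepatotoxicity. It gives no lactate cut-off and no confirmation step.

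Section 12.1.3, under Management of Toxicities, covers the same suspicion: "if an investigator suspects – due to symptoms or lab abnormality – lactic acidosis or symptomatic hyperlactatemia, a lactate level should be drawn". If the first lactate is above 2 x ULN, the site is to "obtain a confirmatory lactate value as soon as possible, preferably within 1 week". The stop is attached to that second result: "Study treatment should be discontinued immediately if the confirmatory value remains" above 2 x ULN, "or if the site is unable to obtain a confirmatory value within 1 week". Lactate is then followed until normal, when a new regimen may be built with the protocol team. For a symptomatic value below the cut-off, management relative to 2 x "ULN will proceed at the discretion of the local investigator".

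The section also carries a case definition: "Symptomatic hyperlactatemia will be defined as new, otherwise unexplained and persistent occurrence for >2 weeks of one or more of the following" listed symptoms, together with a raised lactate. It does not say whether this definition is needed before anyone acts.

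**The concern.** Both sections address a participant in whom lactic acidosis is suspected. One tells the site to suspend on the findings. The other sets out a sequence in which the only mandatory stop comes after a second lactate, or after a week without one. Neither mentions the other.

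This is a stopping rule for a reaction that the protocol itself describes as sometimes fatal. A physician who consults only the toxicity-management section finds no instruction to hold treatment while the repeat is awaited. A physician who consults only the warnings section finds an instruction to suspend at once. The same participant could be handled differently depending on which page was read.

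**Working it through.** No statistical formula applies and the protocol gives no figure to reproduce. The check is to apply both sections to one participant taking EVG/COBI/FTC/TAF, the only regimen that 11.1 names. The Executive Summary and section 9.1 plan this regimen for nearly all participants.

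| Situation | Section 11.1 | Section 12.1.3 |
|---|---|---|
| (a) Suspicion, no lactate yet | Suspend | Draw a lactate; no hold stated |
| (b) First lactate > 2 x ULN, repeat pending | Suspend | Repeat, preferably within 1 week; no hold stated |
| (c) Symptomatic lactate < 2 x ULN | Suspend only if the findings are judged suggestive | Investigator's discretion |
| (d) Repeat > 2 x ULN, or none within 1 week | Suspend | Discontinue immediately |

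The stated actions differ in (a) and (b). In (c) they differ only if the findings are judged suggestive, which 11.1 does not define. Both sections stop treatment in (d).

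**Size of the gap in (b).** Start the clock at the first lactate above 2 x ULN.

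- Under 11.1, if that value in a suspected case counts as suggestive, further time on treatment is 0 days.
- Under 12.1.3, the latest point for a mandatory stop is 1 week = 7 days.
- Difference: 7 - 0 = up to 7 days. This is an outer limit, because the repeat is wanted as soon as possible.

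The interval in (a) cannot be sized: 12.1.3 sets no time limit for the first lactate.

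**Does anything else in the protocol settle it?**

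- Section 12.2 asks that Grade 3 and 4 laboratory abnormalities be confirmed "before study drug discontinuation, unless such a delay is not consistent with good medical practice". That concerns repeat testing of graded laboratory values. It does not address suspension on clinical suspicion and does not link 11.1 with 12.1.3.
- Section 13.2 sends the reader to a section 9.0 on toxicity management, but section 9 is Study Treatment. Section 12.3 refers to stopping criteria in a safety monitoring section, and no section has that title. The protocol's own pointers therefore do not establish precedence.
- Where section 12 means a temporary hold it generally says so: 12.1.1.2, 12.1.2.2, 12.2.1.2 and 12.2.2.1 all speak of interrupting treatment. Section 12.1.3 contains no such wording.

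**The case against.** The strongest reply is that the sections can be followed together. Section 11.1 speaks of suspending and 12.1.3 of discontinuing, after which a new regimen may be built. A site that holds treatment on suspicion and discontinues on confirmation complies with both. Nor does 12.1.3 say in words that treatment continues while the repeat is awaited. This stands: the two sections are not irreconcilable orders, and continued treatment is an inference from silence. But the protocol does not set out the two-step reading, and an immediate stop tied to the second result presupposes someone still on treatment.

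A second reply is that section 11 is general warning text and section 12 the working procedure. That is plausible, but no such hierarchy is stated and 11.1 is worded as a directive.

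A third is that other rules limit the harm. Section 12.3 lets the On-Site Principal Investigator stop treatment for any adverse event, and holds or stops it for certain Grade 3 and 4 events. Section 12.1.1.2 interrupts for Grade 3 or worse nausea and vomiting. Under 12.1, Grade 3 and 4 clinical events at both sites go to that one investigator. These provisions reduce the practical exposure, and nothing in 12.1.3 forbids an earlier stop. They do not say what happens between suspicion and confirmation.

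Some stronger readings are tempting but unsupported:

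- A reader might add the symptom period to the repeat window (14 + 7 = 21 days) and infer a delay of about 3 weeks. In 12.1.3 the draw follows from suspicion and the repeat from the first value; neither is made conditional on the symptom definition. The comparison would also mix clocks, since early non-specific symptoms need not trigger 11.1 either.
- A reader might infer that 11.1 suspends for every symptomatic lactate below 2 x ULN. It does not say that a mild rise is suggestive of lactic acidosis.
- The lack of a rule for a value of exactly 2 x ULN is a trivial boundary matter on which nothing here depends.

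**Conclusion.** The point holds as an inconsistency in wording. From the same suspicion, 11.1 calls for suspension without threshold or confirmation, while 12.1.3 requires a stop only after a confirmatory lactate or a week without one. The protocol neither links the sections nor ranks them.

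The supportable size is up to about 7 days on treatment after a first lactate above 2 x ULN, for a site following 12.1.3 alone. This assumes that the participant takes EVG/COBI/FTC/TAF, that the first value counts as suggestive under 11.1, that the site reads the silence in 12.1.3 as permission to continue, and that no other rule prompts an earlier stop.

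A reader might infer that inconsistent interruptions would disturb the cohort's assumption of continuous ART. The protocol does not support that: 12.1.3 expects lactic acidosis to be very rare, and no endpoint, sample size or error rate depends on this rule. The case rests on individual safety, which is reason enough to resolve it. Which section states the right clinical rule is not judged here.

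**What to change.** Reconcile and cross-reference sections 11.1 and 12.1.3 so that one rule states:

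- whether treatment is held while the first lactate or its confirmation is pending;
- whether the symptom definition of more than 2 weeks bears on the stopping decision or only on classifying the event.

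The sponsor's clinicians should choose the content. The cost is a few sentences in an amendment, with no new tests or visits and no change to the analysis.

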11.2 PATIENTS WITH HIV AND HBV COINFECTION

It is recommended that all patients with HIV be tested for the presence of hepatitis B before initiating antiretroviral therapy. Co-formulated EVG/COBI/FTC/TDF or EVG/COBI/FTC/TAF is not indicated for the treatment of chronic HBV infection and the safety and efficacy of these co-formulated regimens have not been established in patients co-infected with hepatitis B virus and HIV. Severe acute exacerbations of hepatitis B have been reported in patients after the discontinuation of emtricitabine and tenofovir DF. Hepatic function should be closely monitored with both clinical and laboratory follow-up for at least several months in patients who discontinue co-formulated EVG/COBI/FTC/TDF or EVG/COBI/FTC/TAF and are co-infected with HIV and HBV.

HIV-1/hepatitis B co-infected individuals will not be enrolled in this study.

